20. Medical condition, serious intercurrent illness, or other circumstance that, in the Investigator's judgment, could jeopardize the candidate's safety as a study subject, or that could interfere with study objectives.

21. For subjects in the UK only: Refusal of permission to allow the subject's General Practitioner to be notified of their participation in the study.

STUDY TREATMENT

Quizartinib

For subjects randomized to quizartinib the starting dose will be 30 mg/day unless the subject is receiving concurrent therapy with a strong CYP3A4 inhibitor, in which case the starting dose will be 20 mg/day. The dose will be taken in the morning with or without food over continuous 28-day cycles. If the subject omits to take quizartinib in the morning, it may be taken later in the day (until midnight), otherwise the dose is considered missed. If the subject vomits after taking quizartinib, no replacement dose should be given.

CYCLE 1 DAY 16

For subjects not taking a strong CYP3A4 inhibitor the dose of quizartinib will be increased from 30 to 60 mg/day starting on Day 16 based on the following criteria:

- The subject's average QTcF, based on triplicate reading, must be ≤ 450 msec on and before Day 15.

For subjects taking a strong CYP3A4 inhibitor, the dose of quizartinib will be increased from 20 mg/day to 30 mg/day providing they meet the above QTcF requirements.

CYCLE 2 DAY 1

Subjects who fail to achieve a CR, CRp, or CRi as defined in Section 7.2 after at least one 28-day cycle of therapy may undergo dose escalation if the following criteria are met:

- Subject has not had dose interruption or dose reduction for a Grade 3 or higher, non-hematologic, and related adverse event.
- No increase in QTcF more than 60 msec above baseline.
- The subject must not have aplastic bone marrow at the time of the proposed dose escalation.

In addition, subjects who achieved a response [CR, CRi, CRp or partial remission (PR)] at any time, and who have subsequently relapsed, may undergo dose escalation provided they meet the same criteria outlined above.

For subjects not taking a strong CYP3A4 inhibitor the dose of quizartinib will be increased to 60 mg/day.

For subjects taking a strong CYP3A4 inhibitor, the dose of quizartinib will be increased to 30 mg/day providing they meet the above requirements.

Following dose escalation, triplicate ECG determinations should be performed at least once weekly for 2 weeks to monitor QTcF prolongation.

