5.1.2. Treatment

A flow chart of study activities is presented in [Figure 1](#).

For subjects randomized to quizartinib the starting dose will be 30 mg/day unless the subject is receiving concurrent therapy with a strong CYP3A4 inhibitor, in which case the starting dose will be 20 mg/day. The dose will be taken in the morning with or without food over continuous 28-day cycles. If the subject omits taking quizartinib in the morning, it may be taken later in the day (until midnight), otherwise the dose should be considered missed. If the subject vomits after

taking quizartinib, no replacement dose should be given. Detailed information on quizartinib dosing is provided in Section 5.6.4.1.

The dose of quizartinib will be increased at Day 16 or Cycle 2 Day 1 according to the criteria specified in Section 5.6.4.3. Following dose escalation, triplicate ECG determinations should be performed at least once weekly for 2 weeks to monitor QTcF prolongation.

If necessary, the dose of quizartinib may be reduced according to the criteria described in Section 5.6.4.4.

See also Section 8.5 for details of QTcF management when prolongation is observed.

[figure not shown]
In subjects receiving quizartinib or LoDAC, treatment should continue until there is no longer clinical benefit from therapy, or until unacceptable toxicity occurs. For subjects receiving LoDAC the initiation of cycles may be delayed for up to 14 days to allow for recovery from toxicity.

Subjects that receive either quizartinib or LoDAC will be assessed for response on Day 1 of Cycle 2 and Day 1 of Cycle 3 as well as on Day 1 of each subsequent cycle unless the subject has already achieved CR, CRp, or CRi. In that event, bone marrow testing will be repeated after every 3 subsequent cycles, unless there is evidence of relapse.

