5.6.4. Selection and Timing of Doses for Each Subject

5.6.4.1. Quizartinib

For subjects randomized to quizartinib the starting dose will be 30 mg/day unless the subject is receiving concurrent therapy with a strong CYP3A4 inhibitor, in which case the starting dose will be 20 mg/day. The dose of quizartinib will be taken in the morning over continuous 28-day cycles. Quizartinib should be taken in the morning. If the subject omits taking quizartinib in the morning, it may be taken later in the day (up to midnight) otherwise the dose is considered missed. If the subject vomits after taking quizartinib, no replacement dose should be given. Criteria for dose escalation or dose reduction are provided in Section 5.6.4.3 and Section 5.6.4.4 respectively.

Quizartinib can be crushed and dissolved in water. The resulting solution can be drawn up in a disposable syringe and administered via polyvinyl chloride or silicone nasogastric tubes. Details can be found in the Pharmacy Manual.

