5.6.4.3. Quizartinib Dose Escalation Rules and Definitions

CYCLE 1 DAY 16

For subjects not taking a strong CYP3A4 inhibitor the dose of quizartinib will be increased to 60 mg/day starting on Day 16 if the subject's average QTcF (QT interval corrected with Fridericia's formula), based on triplicate reading, is ≤ 450 msec on and before Day 15.

For subjects taking a strong CYP3A4 inhibitor, the dose of quizartinib will be increased to 30 mg/day providing they meet the above QTcF requirements.

CYCLE 2 DAY 1

Subjects who fail to achieve a CR, CRp or CRi as defined in Section 7.2 after at least one 28-day cycle of therapy, and may undergo dose escalation providing the following criteria are met:

- The subject has not had a Grade 3 or higher, non-hematologic, and related adverse event.
- No increase in QTcF more than 60 msec above baseline.

- The subject must not have aplastic bone marrow at the time of the proposed dose escalation.

In addition, subjects who achieved a response (CR, CRi, CRp, or PR) at any time and who subsequently relapsed may undergo dose escalation provided they meet the same criteria as above.

For subjects not taking a strong CYP3A4 inhibitor the dose of quizartinib will be increased to 60 mg/day.

For subjects taking a strong CYP3A4 inhibitor, the dose of quizartinib will be increased to 30 mg/day providing they meet the above requirements.

Following dose escalation, triplicate ECG determinations should be performed at least once weekly for 2 weeks to monitor QTcF prolongation.

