5.6.4.4. Quizartinib Dose Reduction Rules and Definitions

The dose of quizartinib will be reduced stepwise from 60 mg/day to 30 mg/day or from 30 mg/day to 20 mg/day, based on the following criteria:

QTcF (QT interval corrected with Fridericia's formula) Prolongation

- Grade 2 (QTcF average of triplicate readings > 480 msec)
 - The dose will be reduced without interruption.
 - If 20 mg/day is the current dose, dosing will be interrupted for up to 14 days. If QTcF returns to within 30 msec of baseline or ≤ 450 msec within 14 days, treatment may be resumed at 20 mg/day.
- Grade 3 (QTcF average of triplicate readings > 500 msec)
 - Dosing will be interrupted for up to 14 days. If QTcF returns to within 30 msec of baseline or ≤ 450 msec within 14 days, treatment may be resumed at a reduced dose.
 - If 20 mg/day is the current dose, dosing will be interrupted for up to 14 days. If QTcF returns to within 30 msec of baseline or ≤ 450 msec within 14 days, treatment may be resumed at 20 mg/day. If Grade 3 event returns, treatment will be discontinued.
- Grade 4 (QTcF >500 msec or >60 msec change from baseline, and Torsade de pointes or polymorphic ventricular tachycardia or signs/symptoms of serious arrhythmia)
 - Treatment will be discontinued.

See Section 8.5 for clinical guidelines for the management of QT prolongation.

Non-hematologic Toxicity

Grade 3 or 4 related to quizartinib and persisting >48 hours without improvement to \leq Grade 2.

- Dosing will be interrupted for up to 14 days.

- If toxicity improves to \leq Grade 1 within 14 days, treatment may be resumed at the reduced dose.

Myelosuppression

In a subject with CRp or CRi, the dose may be reduced at the Investigator's discretion if:

- The subject has been treated for a minimum of 2 cycles.
- Platelet count is $<100 \times 10^9/L$ and ANC is $\leq 1000 \times 10^9/L$.
- Marrow blast count is $<5\%$.
- There is no evidence of extramedullary disease.

Initiation of concomitant treatment with a strong CYP3A4 inhibitor is identified in [Appendix 1: List of Potential QT Prolonging Drugs, CYP3A4 Inhibitors/Inducers, and P-glycoprotein Inhibitors/Inducers](#).

The dose will be reduced one level (60 mg to 30 mg or 30 mg to 20 mg) when treatment with a strong CYP3A4 inhibitor is initiated.

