6.2.2.5. Cycle 2, Day 1 (± 3 days)

The following activities will take place during this visit:

- Physical examination
- Vital sign determinations
- ECOG performance status evaluation
- Review of concomitant medications

- 12-lead ECG (triplicate) before dosing and 2 to 4 hours after dosing
- Collection of samples obtained before dosing for clinical laboratory tests (hematology, chemistry, and urinalysis)
- Bone marrow aspiration and biopsy for local determination of response; biopsy may be omitted if aspirate sufficient.
- AE/SAE evaluation
- Collection of blood samples for PK determinations before dosing and 2 to 4 hours after dosing. When an ECG is performed at the same study time point, the PK specimen should be taken immediately afterwards.
- Administration of quizartinib at the study site
- Review of returned study medication and assessment of compliance
- Consideration of whether a dose escalation is required if it did not occur at Day 16 (following results from bone marrow aspiration and morphology)

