13.4. Primary Efficacy Analysis

Primary efficacy analysis will take place after the required number of events (deaths), 140 events (deaths) at the interim analysis or 280 events (deaths) at the final analysis, has occurred.

The primary efficacy endpoint (OS) analysis will be based on the stratified log-rank test. The stratification factors will be those used for randomization. A non-stratified log-rank test will be used as supportive evidence of efficacy. These analyses will be performed on the intent-to-treat (ITT) analysis data set, consisting of data from all subjects randomized.

Kaplan-Meier methods will be used to estimate OS in each treatment group, both overall and within subsets of subjects defined by the stratification factors. Estimates of median survival will be provided with 95% confidence intervals. Hazard ratio estimates will also be presented.

Overall survival will be censored at the last date when subjects were known to be alive. For primary analysis, overall survival will not be censored at the time of subsequent non protocol AML therapy, including transplantation.

Sensitivity analyses of OS will be performed by implementing an additional censoring rule: censoring at the date of HSCT for all subjects who have undergone HSCT. The sensitivity analyses will be described in detail in the statistical analysis plan. The primary efficacy analysis will be repeated for the per protocol set (PPS), which includes all subjects who are randomized and have no major protocol deviations.

Protocol deviations will be reviewed in a blinded fashion and categorized as major or minor before the interim analysis and data base lock and will be documented in a memo.

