14.7. Protocol Deviations

Protocol deviations include all important deviations related to study inclusion or exclusion criteria, study conduct, subject management, or subject assessment. Major protocol deviations must be reported to the Sponsor or its designee and to the IRB/IEC. Examples of protocol deviations include:

- Randomization of subjects not satisfying entry criteria
- Failure to withdraw subjects meeting withdrawal criteria
- Administration of the wrong treatment or an incorrect study drug dose

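### The synopsis sets a looser toxicity bar for the Cycle 2 Day 1 quizartinib dose increase than Section 5.6.4.3 does

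*Combined protocol and SAP*

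**What the plan says.** Two places list the conditions for raising quizartinib at Cycle 2 Day 1 in subjects without CR, CRp or CRi. Both apply the same list to responders who later relapse.

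- **Synopsis, Study Treatment, Cycle 2 Day 1:** "Subject has not had dose interruption or dose reduction for a Grade 3 or higher, non-hematologic, and related adverse event".
- **Section 5.6.4.3:** "The subject has not had a Grade 3 or higher, non-hematologic, and related adverse event".

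The other two conditions match: QTcF no more than 60 msec above baseline, and a marrow that is not aplastic.

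The body treats Section 5.6.4.3 as the source of the rule. Section 5.1.2 states: "The dose of quizartinib will be increased at Day 16 or Cycle 2 Day 1 according to the criteria specified in Section 5.6.4.3". Section 5.6.4.1 states: "Criteria for dose escalation or dose reduction are provided in Section 5.6.4.3 and Section 5.6.4.4 respectively". Section 5.2.3 and the dosing footnote to Table 3 point there too. The synopsis sets out its own list and does not refer to Section 5.6.4.3.

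Section 5.6.4.4 says when non-hematologic toxicity interrupts dosing: "Grade 3 or 4 related to quizartinib and persisting >48 hours without improvement" to Grade 2 or lower. The synopsis carries the same trigger.

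**The concern.** The synopsis looks at what the event did to the dose, and Section 5.6.4.3 looks at whether the event happened. If every related Grade 3 or worse event forced a dose change, the two would be equivalent. The 48-hour condition means that not every such event does.

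The risk runs one way. Escalation at this step is optional under both texts, so holding the dose complies with either. A site working from the synopsis, however, could raise a dose that Section 5.6.4.3 prohibits. Section 14.7 gives this example of a protocol deviation: "Administration of the wrong treatment or an incorrect study drug dose". With two current criteria, whether such a case is a deviation could be disputed. The per-protocol set in Section 13.4, "which includes all subjects who are randomized and have no major protocol deviations", would be touched only if the blinded review classed the deviation as major.

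**Working it through.** No alpha, power, event count or sample size enters, so the check compares the rules case by case.

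**Step 1: who is barred from the Cycle 2 Day 1 or post-relapse increase.** All rows concern a related non-hematologic event.

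| Event | Dose change required by Section 5.6.4.4? | Synopsis | Section 5.6.4.3 |
|---|---|---|---|
| Grade 3 or 4, lasting more than 48 hours without easing to Grade 2 or lower | Yes, interruption | Barred | Barred |
| Grade 3 QTcF prolongation | Yes, interruption | Barred | Barred |
| Grade 3 or 4, eased to Grade 2 or lower within 48 hours, dose unchanged | No | **Allowed** | **Barred** |

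Everyone barred by the synopsis is also barred by Section 5.6.4.3, but the reverse fails in the last row. The synopsis is therefore strictly looser.

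**Step 2: who can fall in the last row.** A subject in the quizartinib arm must meet all of these:

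1. Below target dose (60 mg/day, or 30 mg/day with a strong CYP3A4 inhibitor). The Day 16 increase is the default when QTcF is 450 msec or less, and Section 6.2.2.5 frames the Cycle 2 Day 1 decision as "Consideration of whether a dose escalation is required if it did not occur at Day 16". Subjects already at target have no further step.
2. No CR, CRp or CRi, or relapsed after a response.
3. A related non-hematologic event of Grade 3 or worse with no dose change.
4. QTcF rise of 60 msec or less.
5. A marrow that is not aplastic.

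The only ceiling the documents supply is the planned arm size, 242. They give no frequency for the combination, so none is estimated.

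**Step 3: the dose step in dispute.**

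- No strong CYP3A4 inhibitor: 60 / 30 = 2.0-fold.
- With a strong CYP3A4 inhibitor: 30 / 20 = 1.5-fold.

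These are nominal dose ratios, not measures of added risk.

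**The case against.** The best reply is that the documents already show which rule operates. Several body sections send the reader to Section 5.6.4.3, and the synopsis is a summary. Harm requires a site to dose from the synopsis despite those pointers. This is fair, and it is the main reason the point is minor. It does not remove the contradiction: no clause gives the body precedence, and the Cycle 2 Day 1 visit list in Section 6.2.2.5 does not itself cite Section 5.6.4.3.

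A second argument concerns the separate re-escalation rule in the synopsis and at the end of Section 5.6.4.4. A subject on a reduced dose may go back up once the responsible toxicity has resolved to Grade 1 or lower, except after Grade 3 QTcF prolongation. A subject with a worse, dose-reducing event thus has a route upward, while one with a brief Grade 3 event and no dose change has none under the strict wording. The oddity is real and should be looked at when the wording is settled. It does not resolve the mismatch, because re-escalation covers only subjects on a reduced dose and the disputed cases had no reduction. The statement that persistent events are barred under both texts refers only to the Cycle 2 Day 1 and relapse list.

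Third, the route to any effect on an analysis is long: a dose given under the synopsis, then a recorded deviation, then a major classification, then exclusion from the per-protocol set. That also stands, and no effect on the primary analysis is claimed. Section 5.2.3 reports no major overall difference in adverse events between 30 and 60 mg/day in the Phase 2b study, which further limits the likely harm.

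**Conclusion.** The contradiction holds. The synopsis permits a dose increase that Section 5.6.4.3 forbids after a related non-hematologic event of Grade 3 or worse that caused no dose change. Severity is minor: the affected group is narrow and of unknown size, the operative section can be identified, and neither the intent-to-treat survival analysis nor the design's error rates, power and event count are touched. It still merits correction because it is a live safety condition on dosing and the error can only run towards a higher dose. The conclusion rests on reading both texts as current and on the 48-hour trigger, which is the same in the synopsis and in Section 5.6.4.4.

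**What to change.** Replace the synopsis bullet with the Section 5.6.4.3 wording: "The subject has not had a Grade 3 or higher, non-hematologic, and related adverse event". This is the protective choice and the one the cross-references support. If the sponsor's clinical team confirms that the looser rule was intended, amend Section 5.6.4.3 instead. Either way, read the chosen wording against the re-escalation rule in Section 5.6.4.4 before issuing it.

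The cost is one sentence, by clarification letter or at the next amendment. Section 14.3 requires prior ethics approval for changes that are not logistic or administrative. Aligning the synopsis with the operative section is easier to class as administrative than loosening Section 5.6.4.3 would be. Sample size, data collection, the deviation and per-protocol rules, and the analysis all stay as they are.

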8.4. Electrocardiograms

Supine triplicate 12-lead ECGs will be obtained at the times specified in the study schedule (Section 5.8). Additional ECGs may be obtained at the Investigator's discretion. Subjects undergoing dose escalation due to lack of response or loss of response after cycle 2 day 1 should be monitored carefully for QT prolongation which should include at least weekly ECGs for 2 weeks.

Electrocardiograms will be recorded in triplicate (3 separate ECGs at least 3 minutes apart but preferably no more than 5 minutes apart; the average of the 3 QTcF determinations will be used to determine safety parameters and dose escalation at Day 16 day of quizartinib administration) and transmitted electronically to a central ECG laboratory. Electrocardiograms will be reviewed by a suitably-qualified physician at the study site to allow immediate decisions about subject safety. When an ECG abnormality of concern is suspected (eg, QTcF >480 msec), the site will

contact the central ECG laboratory to obtain an expedited (within 24 hours) evaluation, and the site will use the central laboratory's analysis for decisions on changes in subject care and protocol compliance. The ECG should be repeated in triplicate within 2 hours on the same day for analysis by the central laboratory. Results of the central ECG laboratory analysis will be the final data for the ECG database. Electrocardiograms will be submitted to the FDA ECG warehouse, if required by the FDA. QTcF duration will be used to make all decisions based on QT criteria.

Guidelines for ECG monitoring are as follows:

- Electrocardiograms will be obtained after the subject has rested quietly and is awake and fully supine for 10 minutes before the first of the triplicate ECGs.
- Additional ECGs can be obtained at any time if clinically indicated. It is important to record actual clock time for each assessment. The triplicate ECGs will be recorded and the average QTcF interval will be determined for each time point.

If clinically significant ECG changes from baseline at screening are noted, the changes will be recorded as AEs on the appropriate CRF. Clinically significant changes will be defined as any ECG variations that are medically significant and could cause a change in medical care. The Investigator must continue to monitor the subject until any ECG changes return to normal.

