8.5. Management of QT Prolongation

Quizartinib is known to be associated with prolongation of the QT interval. To reduce the risk of cardiac arrhythmias, it is important to maintain serum electrolytes (K^+ , Ca^{++} , and Mg^{++}) within normal range and ideally maintain K^+ above 4.0 mEq/L. Subjects in the quizartinib arm who experience QTcF prolongation \geq Grade 2 should be managed according to the guidelines below.

- Grade 2 (QTcF average of triplicate readings > 480 msec)
 - Electrolytes (potassium, calcium and magnesium) should be checked and supplementation given to correct any values outside the normal range
 - Concomitant medications should be reviewed to identify and, if appropriate, discontinue any medication with known QT prolonging effects
 - The dose of quizartinib will be reduced one level without interruption of dosing
 - Quizartinib dose may be re-escalated after 1 cycle at reduced dose if QT prolongation has decreased to \leq Grade 1 but subject must be monitored closely for QT prolongation for first cycle at the increased dose.
- Grade 3 (QTcF average of triplicate readings > 500 msec)
 - Electrolytes (potassium, calcium and magnesium) should be checked and supplementation given to correct any values outside the normal range
 - Concomitant medications should be reviewed to identify and, if appropriate, discontinue any medication with known QT prolonging effects
 - Quizartinib dosing will be interrupted for up to 14 days. If QTcF returns to within 30 msec of baseline or ≤ 450 msec within 14 days, treatment may be resumed at a

reduced dose. Quizartinib dose cannot be escalated following dose reduction for Grade 3 QTcF prolongation.

- Grade 4 (QTcF average of triplicate readings >500 msec or >60 msec change from baseline, and Torsade de pointes or polymorphic ventricular tachycardia or signs/symptoms of serious arrhythmia)
 - Electrolytes (potassium, calcium and magnesium) should be checked and supplementation given to correct any values outside the normal range
 - Concomitant medications should be reviewed to identify and, if appropriate, discontinue any medication with known QT prolonging effects
 - Quizartinib dosing will be permanently discontinued.

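### The myelosuppression dose-reduction rule prints an ANC limit 1000 times too high; secondarily, the later escalation criteria would be clearer with a 480 msec QTcF ceiling

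*Combined protocol and SAP*

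**What the plan says.** **Myelosuppression reduction.** The synopsis and Section 5.6.4.4 allow a dose reduction, at the investigator's discretion, in a subject in CRp or CRi. All of the following must hold: at least 2 cycles given, platelets below 100 x 10^9/L together with ANC at or below 1000 x 10^9/L, marrow blasts below 5%, and no extramedullary disease. Elsewhere the neutrophil cut-off is 1 x 10^9/L: for restarting quizartinib after HSCT (Section 5.6.4.5), for CR (Section 7.2.1) and for CRi (Section 7.2.3).

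**QTcF and escalation.** On Day 16 of Cycle 1 the criterion is absolute: 450 msec or less. At Cycle 2 Day 1 (synopsis and Section 5.6.4.3) it is relative: "No increase in QTcF more than 60 msec above baseline". The same list bars subjects with a related Grade 3 or higher non-hematologic adverse event (in the synopsis, one that led to interruption or reduction) and subjects with an aplastic marrow. The list is reused after loss of response, for subjects "who subsequently relapsed may undergo dose escalation provided they meet the same criteria as above". Section 5.4.2 excludes a QTcF above 450 msec at entry.

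**QTcF and reduction.** Section 5.6.4.4 defines "Grade 2 (QTcF average of triplicate readings > 480 msec" as a trigger for lowering the dose without a break, or for interrupting it when the current dose is 20 mg/day. Section 8.5 repeats this: "The dose of quizartinib will be reduced one level without interruption of dosing". After such a reduction, "Quizartinib dose may be re-escalated after 1 cycle at reduced dose if QT prolongation has decreased to" Grade 1 or lower. The synopsis introduces its reduction list as mandatory whenever any criterion in it is met.

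**The concern.** The ANC limit is a decision threshold in an operative dosing rule. If every subject meets it, the rule drops one of its two blood-count conditions. A subject in CRp or CRi with a normal neutrophil count and platelets below 100 x 10^9/L then qualifies for discretionary reduction, provided the other conditions hold. Because platelets and ANC are joined by *and*, the rule reads as one for joint cytopenia, but in effect it acts on platelets alone.

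The QTcF point concerns consistency between two lists. QT prolongation is this drug's known dose-dependent risk (Section 5.2.3), and Table 3 footnote j sends sites to Section 5.6.4.3 for the escalation criteria. That list contains no absolute QTcF limit for the later escalations. Read alone, it can be satisfied at a reading where another section requires the dose to come down.

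**Working it through.** There is no sample size, power or alpha figure to reproduce here; the check is threshold arithmetic.

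**1. ANC units.** One litre is 10^6 microlitres.

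- As printed: 1000 x 10^9 / 10^6 = 1,000,000 cells per microlitre.
- Cut-off used elsewhere: 1 x 10^9 / 10^6 = 1000 cells per microlitre.
- Ratio: 1000 / 1 = 1000.

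The likely cause is that the per-microlitre number was paired with the per-litre unit. The value appears in both the synopsis and Section 5.6.4.4, so text extraction is an unlikely explanation.

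| Subject in CRp or CRi, platelets <100 x 10^9/L, other conditions met | As printed | With 1 x 10^9/L |
|---|---|---|
| ANC at or below 1 x 10^9/L | qualifies | qualifies |
| ANC above 1 x 10^9/L | qualifies | does not qualify |

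**2. QTcF overlap.** Inputs: maximum entry QTcF 450 msec (Section 5.4.2), permitted rise 60 msec (Section 5.6.4.3), Grade 2 above 480 msec and Grade 3 above 500 msec (Section 5.6.4.4). I take baseline to lie within the entry limit.

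- Highest reading that passes the escalation criterion at baseline b: b + 60.
- Overlap with the reduction rule needs b + 60 > 480, so b > 480 - 60 = 420 msec.
- Readings above 500 msec pass the 60 msec criterion only if b > 440. They are Grade 3, must be recorded as adverse events (Section 8.5) and, if judged related, are barred by the adverse-event criterion.
- Remaining band: above 480, up to the lower of 500 and b + 60. For b from 420 to 450 its width is min(20, b - 420).

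| Baseline (msec) | Highest passing reading (msec) | Width of band (msec) |
|---|---|---|
| 420 | 480 | 0 |
| 425 | 485 | 5 |
| 430 | 490 | 10 |
| 440 | 500 | 20 |
| 450 | 510 | 20 (500 msec cap applies) |

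**3. How often.** Table 2 gives 5% of the Phase 2b 30 mg group (N = 38) with a maximum QTcF above 480 and up to 500 msec, about 2 subjects (0.05 x 38 = 1.9). This is a whole-study maximum at any baseline, in a group where 63% escalated to 60 mg. It does not count subjects meeting both rules at an escalation decision. Baseline QTcF is not reported, so that number cannot be derived.

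**4. Could a first crossing occur at Cycle 2 Day 1?** Take a constant dose and the half-life of about 3 days in Section 3.3.

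- Before dosing on Day 15: 14/3 = 4.67 half-lives; 1 - 2^-4.67 = 0.961 of steady state.
- Before dosing on Day 29: 28/3 = 9.33 half-lives; 1 - 2^-9.33 = 0.998.
- Ratio: 0.998 / 0.961 = 1.04.

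Accumulation adds only about 4%, so a first reading above 480 msec at that visit would need another cause.

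**The case against.** On ANC, the best defence is that the slip is obvious, sits in a discretionary rule and cannot cause unsafe escalation. That limits the consequence, but it does not make the printed threshold right. A reader might go further and infer that *and* is also an error, since a subject currently meeting CRp has ANC above 1 x 10^9/L and would drop out of the corrected rule. The documents do not show that. Section 3.3 reports delayed recovery or continued suppression of both neutrophils and platelets under continued treatment, so a rule for joint cytopenia after at least 2 cycles is coherent. It would reach a CRp subject whose ANC later fell. The conjunction is at most a query to the sponsor.

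On QTcF, a reader might infer that the protocol permits, or even directs, escalation where it requires reduction. Section 5.1.2 seems to invite this: "The dose of quizartinib will be increased at Day 16 or Cycle 2 Day 1 according to the criteria specified in Section 5.6.4.3", whereas "If necessary, the dose of quizartinib may be reduced according to the criteria described in Section 5.6.4.4". The documents do not support that reading. Both sentences defer to the operative sections, and Section 5.1.2 then points to Section 8.5. The synopsis makes reduction mandatory once any criterion is met; Sections 5.6.4.4 and 8.5 repeat the obligation above 480 msec. Eligibility for the later escalations is permissive. A subject already reduced for a Grade 2 reading falls under the re-escalation limits. Section 8.4 adds a further check: "When an ECG abnormality of concern is suspected (eg, QTcF >480 msec), the site will" seek expedited central evaluation, with a repeat triplicate ECG within 2 hours.

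A reader might also take the 4/38 (11%) in Section 5.2.3 as the size of the problem. That figure includes readings above 500 msec; Table 2 gives 5% for the band itself.

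What stands is narrow: the escalation list does not itself contain the limit that the reduction list imposes. Causes other than accumulation are possible, because Section 5.6.6.1 permits QT-prolonging drugs when essential and moderate CYP3A4 inhibitors without dose reduction.

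**Conclusion.** The ANC threshold is wrong as written, by a factor of 1000, in both places where the rule appears. As printed, ANC has no influence on the decision. This rests on reading 1 x 10^9/L as the intended value, which the protocol's other neutrophil cut-offs support.

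The QTcF part is a clarification. The two lists overlap for baselines above 420 and up to 450 msec at readings above 480 and up to 500 msec. The mandatory reduction rule reasonably governs there, and few subjects are likely to be affected.

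Severity: minor. Neither part touches the sample size, the endpoints or the OS analysis.

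**What to change.** 1. In the synopsis and Section 5.6.4.4, change the myelosuppression threshold to ANC at or below 1 x 10^9/L (1000 per microlitre). When making the change, ask the sponsor to confirm that joint cytopenia is intended.
2. In the synopsis and Section 5.6.4.3, add to the Cycle 2 Day 1 criteria, which also serve escalation after relapse: QTcF no more than 480 msec (average of triplicate readings). No reading can then satisfy the escalation criteria while triggering a QTcF reduction. The level matches what Section 8.5 implies for re-escalation after a Grade 2 reduction.
3. Do not use 450 msec instead. It is already the Day 16 condition, and repeating it would remove much of the second escalation opportunity described in Table 3 footnote j.

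The cost is a short protocol amendment, with IRB/IEC approval as Section 14.3 requires. The QTcF ceiling adds no restriction beyond what the reduction rule already imposes.
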